7.2.2. Enrollment

The participant is considered enrolled into the study after providing written consent and is found eligible based on history, eligibility screening questions, and confirmation as a participant in the CFFPR. Eligible consented participants who withdraw consent for any reason before completing the survey are considered screen failures. Eligible consented participants who cannot be verified as a participant in the CFFPR with a CFFPR ID number (confirmed by respective CF center) will be considered a screen failure.

7.3. Interventions

We will provide an online questionnaire to give to female participants in order to obtain exposure data (past contraceptive use). We will have participants complete the survey on their own, either in clinic or at home. The survey will include pictures, brand names, and descriptions to help respondents remember birth control method used retrospectively.

We will ask each CF center to provide DXA scan results for 10 participants (selected at random) from their respective EMRs in order to validate osteoporosis, osteopenia and bone fracture information in the CFFPR.

7.3.1. Treatment

N/A

7.4. Interventions: Modifications

N/A.

7.5. Outcomes (include DAG diagrams to show relationships between exposure and outcomes)

Table 5: Outcomes and associated confounders and covariates

Exposure of interest	Outcome	Confounders/Covariates	Rationale
Combined	Pulmonary outcomes	Smoking	Affects lung function
hormonal contraception (CHC)	 Annual pulmonary exacerbation rate (PEx) (defined as episodes requiring intravenous 	Insurance status (reflection of SES)	Will be used as socioeconomic indicator. Less access to meds may mean less
&	antibiotic use at home or in		compliance
Progestin-only	hospital)Absolute change in FEV1 (in	Age	Lung function worsens as one ages
contraception	liters) Prevalence of micro-organism (defined as 1 or greater sputum	Education (reflection of SES)	Affects contraceptive knowledge decision making
	culture within a 12-month period)P. aeruginosa	ВМІ	Associated with better or worse health status in general

Exposure of interest	Outcome	Confounders/Covariates	Rationale
	 MDR P. aeruginosa Staph aureus 	Exercise	May reduce pulmonary exacerbation rates
	MSSA MRSA	CF genotype class	Associated with severity of disease
	Secondary infections: • Burkholderia cepacia	CFTR modulator treatment	Likely preserves pulmonary decline
	 Burkholderia cenocepacia Mycobacterial species –includes M. tuberculosis and NTM species 	Comorbidity with CFRD (defined as requiring chronic insulin therapy) (11)	Associated with worse disease (reduced immunity)
		Length of hormonal contraceptive use (person-year of exposure)	
	Venous/arterial thromboembolism (VTE)	BMI ≥ 30	
	 Noted on self-respondent survey (defined as blood clot requiring anticoagulation treatment) 	Age > 35 years PMHx for thrombophilia Arterial/venous lines or ports Pmhx cancer Smoking	
	Liver outcomes	BMI	Obesity contributes to
	 Liver disease, non-cirrhosis Gallstone, requiring surgery/procedure (defined as present or absent as 	Comorbidity with diabetes	liver dysfunction Associated with worse disease (reduced immunity)
	recorded in CFFPR)	Hepatitis	Risk factor for liver dysfunction
		CF genotype class Length of hormonal contraceptive use (person-year of exposure)	
	 Serum ALT, GGT (meets criteria if hepatic transaminases and GGT levels exceed upper limit of normal on at least 3 consecutive occasions over 12-month period) (12) 		Will track meeting criteria annually over time
	CF-related diabetes		
	 Serum ogtt trends New onset insulin resistance or diabetes (defined as 		

Exposure of interest	Outcome	Confounders/Covariates	Rationale
	present or absent as		
	recorded in CFFPR)		
	Nutritional status	CF genotype class	
	Change in BMI	CF-specific vitamins (Fat soluable A, D and E) (defined as	
		present or absent as recorded in CFFPR)	
		Taking any pancreatic enzyme replacement therapy (noted under medications in CFFPR)	
		CFTR modulator use (will stratify by type of modulator)	
	Bone outcomes	Length of oral steroid use	Contributes to bone
	Osteoporosis, fragile bone	(person-months of use)	weakening
	fracture	Comorbidity with pancreatic insufficiency	Reduced Vit D/Calcium absorption
		Exercise	Help prevents osteoporosis
		Age	Known risk factor for osteoporosis
		BMI	Reduced BMI is a risk factor for osteoporosis
		CF genotype class	
		Length of hormonal	1
		contraceptive use (person-year	
		of exposure)	
		Smoking	Known risk factor for osteoporosis

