3.0. Hypothesis

- Estrogen-containing methods, but not progestin-only methods, reduce the annual rate of pulmonary exacerbations, the microorganisms associated with a more rapid decline in lung function, and improve ppFEV1 (or absolute FEV1) of women with CF when compared to women with CF who use non-hormonal contraception (control group).
- Estrogen-containing oral methods of birth control are associated with higher incidence of gallbladder disease (defined as gallstones, requiring surgery), increased liver function enzyme values, and/or increased incidence of thromboembolism among women with CF.
- Both estrogen-containing and progestin-only hormonal methods improve BMI among women with CF, which is linked to nutritional status.
- The strength of agreement between DXA scan T-scores and CFFPR data about osteoporosis, osteopenia and bone fracture will be "substantial."
- The effectiveness of oral birth control is reduced compared to other methods of hormonal birth control in the presence of CFTR modulator use.
- Hormonal birth control use results in a greater proportion of patients with mucoid *Pseudomonas aeruginosa*, in patients who are *P. aeruginosa* positive, compared to non-hormonal contraceptive users.

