4.0. Study Objectives

4.1. Primary Study Objective

• To assess the association of hormonal contraceptive use on frequency of pulmonary exacerbations, compared to non-hormonal contraceptive users (primary control) and non-contraceptive users (secondary control).

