9.3. Statistical Methods

Because this is a retrospective cohort study, we are most interested in determining whether this exposure (to hormonal contraception) is associated with our primary outcome (counting the number of pulmonary exacerbations requiring additional IV in a given year) and/or our secondary outcomes (new respiratory microbiology, liver disease/non-cirrhosis, gallstone, requiring surgery/procedure, improved BMI, incidence of VTE, osteoporosis and fragile bone fracture). Women on hormonal contraception will be compared to the primary control group of women on non-hormonal contraception. We will also compare to women on no contraception, as the secondary control group. We will exclude persons with these existing diagnosis at the start of the follow up period for outcome data (January 1, 2010). Within this objective we will be able to calculate incidence rates, relative risks and confidence intervals. We will use Poisson regression to calculate progestin-only and combined hormonal method to non-hormonal method pulmonary exacerbation rate ratios and 95% confidence intervals. This allows for adjustment of follow-up time of each individual.

(Objective 1a): We will evaluate lab values over time (ppFEV1%, serum AST, ALT, alkaline phosphatase) to determine if trends between hormonal contraceptive users and non-hormonal contraceptive users differ. See Table 5 for confounders and covariates that we will use to adjust for the primary and secondary outcomes.

We will model ppFEV1 via generalized estimating equations (GEE), allowing for correlation within a subject, and compare via a fixed effect for exposure. Among women who change or stop contraception, we will estimate and compare within-participant difference in outcomes via the model (if numbers allow). We will censor women who switch method types or become pregnant, and for 6 months post pregnancy, for the primary analysis and subsequently follow them to leverage within-patient data and analyze changes in pulmonary status and contraception. Presence of respiratory microbiology will be estimated longitudinally via GEE with a logit link function. Graphic displays and summary statistics will be used; all *p* values will be two-sided.

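### Table 5 adjusts for length of hormonal use, which is part of the exposure in every contrast with women not using hormonal methods

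*Combined protocol and SAP*

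**What the plan says.** Table 5 (Section 7.5) names combined and progestin-only contraception as the exposures. Its column of confounders and covariates includes "Length of hormonal contraceptive use (person-year of exposure") for the pulmonary and liver outcomes, and the same item again ("Length of hormonal" and so on) for the bone outcomes. None of the three entries has a rationale, although most neighbouring items do. The item is not listed for thromboembolism or nutritional status.

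Section 9.3 gives the table its role: "See Table 5 for confounders and covariates that we will use to adjust for the primary and secondary outcomes". It also sets the primary model: "We will use Poisson regression to calculate progestin-only and combined hormonal method to non-hormonal method pulmonary exacerbation rate ratios". Women on no contraception form a second control group. Person-time is handled separately ("This allows for adjustment of follow-up time of each individual"), and "We will censor women who switch method types or become pregnant" applies to the primary analysis.

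The primary objective in Section 4.1 is "To assess the association of hormonal contraceptive use on frequency of pulmonary exacerbations, compared to non-hormonal contraceptive users (primary control"), and Section 3.0 expects that "Estrogen-containing methods, but not progestin-only methods, reduce the annual rate of pulmonary exacerbations".

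The plan gives no model formula, no coding for length of use and no dose-response model. It does not say what value a control takes.

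**The concern.** A confounder is something other than the exposure that differs between the groups and affects the outcome. Length of hormonal use is not that in a hormonal versus non-hormonal comparison. It measures how much exposure a user has had, and a woman who never used a hormonal method has none.

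If it enters next to the group indicator as an ordinary linear term, the group coefficient describes a hormonal user with no time on the method. Any part of the effect that builds with use goes to the duration term and out of the reported rate ratio. Even when the effect does not depend on duration, the group coefficient becomes an extrapolation to zero and loses precision.

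The class comparison in Section 3.0 is also exposed. If both hormonal classes share one duration slope, a slope produced by one class is imposed on the other.

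**Working it through.** **Inputs.** From Section 7.7: 0.8 exacerbations per year, rate ratio (RR) 0.70, 575 enrolled, 15% attrition, about half on hormonal methods. Analysed women: 575 × 0.85 = 488.75, taken as 489. Assumed, because the documents do not give them: duration among users (mean/SD 4/3 years, also 3/2 and 5/4), outcome years per woman (1, 3 or 5), between-woman variance of the rate (0, 0.5 or 1.0) and the shape of the effect.

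**The plan's own power figure.** For two equal groups and one year each, power = Φ(|ln RR|/SE − 1.96), with SE² = 1/(n₀ × 0.8) + 1/(n₁ × 0.56). At N = 475, SE² = 1/190 + 1/133 = 0.01278 and power is 0.88. Table 8 gives 0.80. The table is matched only with an unstated input, such as overdispersion of about 1.27. At 489, Table 8 interpolates to 0.81 and this formula gives 0.89. The powers below are therefore more optimistic than Table 8. The point does not depend on this, because the SE ratio and the shift in the RR do not come from Table 8.

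**What the coefficient means.** Write log rate = a + b·A + c·d + log(follow-up time), with A = 1 for hormonal users, d = years of use, and d = 0 in controls. The log RR at duration d is b + c·d, so exp(b) is the RR at d = 0.

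**Precision, constant effect.** Without d, Var(b) = 1/I₀ + 1/I₁. With d, Var(b) = 1/I₀ + (1/I₁)(1 + (mean/SD)²). Here I₁ = 0.7·I₀. For 4/3 years:

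SE ratio = √{[1 + (1 + (4/3)²)/0.7] / [1 + 1/0.7]} = √(4.968/2.429) = 1.43.

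For 3/2 and 5/4 years it is 1.52 and 1.39. Simulated power across the three duration assumptions:

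| Counts | Outcome years | Power without d | Power with d |
|---|---|---|---|
| Pure Poisson | 1 | 0.89–0.90 | 0.55–0.64 |
| Pure Poisson | 3 | 1.00 | 0.95–0.98 |
| Pure Poisson | 5 | no loss | no loss |
| Variance 0.5 | 3 | 0.97–0.98 | 0.74–0.82 |
| Variance 0.5 | 5 | 0.99 | 0.85–0.90 |

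**Estimate, by effect shape** (Poisson regression, robust SE, plain d term):

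| True effect | RR without d | RR with d |
|---|---|---|
| Constant 0.70 | 0.70–0.71 | 0.70–0.71 |
| Reaches 0.70 by year 1 | 0.71–0.72 | 0.72–0.74 |
| Reaches 0.70 by year 2 | 0.73–0.74 | 0.78–0.79 |
| Reaches 0.70 by year 3 | 0.75 | 0.82 |
| Linear, 0.70 at mean duration, no ceiling | 0.71–0.73 | 1.00–1.01 |

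**Three groups** (122 combined, 122 progestin-only, 245 non-hormonal). With the linear combined-method effect, no progestin-only effect and one shared slope, combined moves from 0.70–0.73 to 0.80–0.84. Progestin-only moves from 0.99–1.01 to 1.13–1.15. With a separate slope for each class, progestin-only stays at 0.99–1.02, but combined goes to about 1.00.

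**Other codings.** Centred among users, the RR is 0.69–0.71 with no loss of precision. In three bands (under 2, 2 to under 5, 5 or more years), the linear case gives 0.85–0.92. With log(1 + years) it gives 1.20–1.25.

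**Past use in controls.** If 15%, 30% or 50% of controls have earlier use that is counted but has no lasting effect, the linear-case RR with d is 0.87, 0.82 or 0.78, so the shift is smaller.

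**The case against.** The best defence is that the documents do not fix the harm. The column mixes confounders with covariates, the item has no rationale, and its unit resembles person-time. A descriptive or person-time reading would cause no bias, and nor would centring when lengths of use are alike. All this is true and limits the size that can be claimed. It does not remove the point. Section 9.3 says Table 5 is used to adjust and deals with follow-up time separately. Length of hormonal use cannot serve as the offset in controls, since log(0) is undefined. No section assigns the item a dose-response role.

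A reader might infer that the plan will erase a real effect. The documents do not support that. The RR of 1.00 follows from assuming an effect that is zero at the start and grows without limit: at 10 years with mean 4, the RR would be 0.7^2.5 = 0.41. Effects that level off are attenuated, not erased.

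A reader might also infer that progestin-only methods will often be falsely declared harmful. Simulated false rejection reaches 44% with equal lengths of use, but only with pure Poisson counts over 5 years. At variance 0.5–1.0 it is 13–16%. Both figures need the linear shape and a slope shared by the two classes, and the plan specifies neither.

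The largest power loss belongs to one outcome year, whereas outcome data run from 2010 to the latest registry year. Zero duration in controls is also not assured: the survey covers use since 2008, and no section limits the non-hormonal group to women who never used a hormonal method. These qualifications stand.

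**Conclusion.** The point holds and is worth correcting before analysis. Followed as written with a plain term, the plan estimates the hormonal effect at zero years of use for the pulmonary, liver and bone outcomes, not the effect of use that Section 4.1 asks about.

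For exacerbations, under the assumed durations, the cost runs from lost precision alone (SE about 1.4 times larger, constant effect), through moderate attenuation (about 0.73 to about 0.79, effect complete by year 2), to the extreme of 1.00 (unlimited linear build-up). With that linear effect and one shared slope, a null progestin-only group moves to about 1.13–1.15. There is no harm if duration is centred among users and lengths of use are alike.

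Duration distribution, effect shape, coding and past use in controls are all assumptions. No size was computed for the liver or bone outcomes. A combined versus progestin-only comparison is outside the objection, because both groups have a length of use.

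**What to change.** In the three Table 5 rows, remove length of hormonal use from the adjustment set for every contrast with non-hormonal users or women on no contraception. State in Section 9.3 that it will be analysed separately as dose-response among hormonal users; a combined versus progestin-only model may keep it. If person-time was meant, say that it is the follow-up-time offset.

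Report past hormonal use in the control groups, and add a sensitivity analysis that excludes those women.

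The cost is three edited rows and a few sentences. No new data are needed, since the survey already asks for start and stop dates, or ages at first and last use. With the term removed, and no lasting effect of past use in controls, the simulated RR is 0.70–0.74 for the constant effect, for effects complete by year 1 or 2, and for the linear effect.

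Downsides:
- There is one extra analysis. Under linear build-up, the slope test among 244 users has power 0.53–0.83 at one outcome year and 0.82–1.00 at three.
- A cumulative effect is reported as an average over the lengths of use in the sample.
- If controls include past users with lasting effects, the contrast is diluted: about 0.76–0.84 instead of 0.72 when 15–50% are past users (linear case). The sensitivity analysis addresses this, with fewer controls.

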5.0. Trial Design

This is a non-randomized, non-interventional, observational cohort design among reproductive-aged women (ages 18-45 years) with CF. This protocol describes a pilot phase, as well as a larger retrospective approach.

We intend to ask about 625 female participants to provide information about their types of past contraceptive use from 2008 through the most recent data available from CFFPR (2018 or 2019). Before initiating our trial among up to 625 respondents, we intend to pre-test the survey questions on our self-respondent questionnaire among as many as 50 women with and without CF through CFF Community Voice, the Cystic Fibrosis Research, Inc. (CFRI), and the Cystic Fibrosis Reproductive and Sexual Health Collaborative (CFReSHC). Pre-testing our survey questions will help ensure contraceptive, pregnancy, and other reproductive health data from respondents for the larger phase of this study are as complete and accurate as possible.

Once the survey has been piloted and revised accordingly, we will collect past contraceptive, pregnancy and other reproductive health data from up to 625 women at 10 different CF centers. We may over-sample by 25 participants because it is possible that some participants from UW, UTSW and National Jewish may have participated in our earlier published study related to contraceptive use and CFFPR (4). Recruiting through the CF centers will help ensure that women with a confirmed diagnosis of CF respond to the finalized survey. We will link respondent self-reported contraceptive and reproductive health data with CFFPR clinical data. We will ask for EMR data from the 10 different CF centers to validate DXA scan results with findings regarding osteoporosis, osteopenia, and bone fracture in the CFFPR. We plan to randomly select about 10 consented subjects from each of the centers for the EMR DXA scan chart review. Because of our need to link questionnaires and clinical case report forms correctly to the same women with CF in the CFFPR clinical data, we need to request identifiable information, including the CFFPR member ID number.

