7.0. Methods: Participants, Interventions, and Outcomes of Final Questionnaire Phase

Once the questionnaire is pretested (anticipated end date of pre-testing is July 2020), the final questionnaire will be revised accordingly prior to initiating the full, larger study.

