7.1. Study Setting

We intend to enroll up to 625 women, aged 18-45 years, at 10 separate CF centers. We may over-enroll the sample by 25 women to account for women who may have participated in the prior contraceptive study in 2017. This will allow us to perform a sensitivity analysis excluding women who participated in the pre-study, while maintaining study power.

Name of Institution	Institution PI(s)	Number of women with CF aged 18-45 years
University of Washington	[name], MPH	141
	[name]	
University of Texas Southwestern	[name], MS	140
National Jewish Hospital	[name], MS	233
University of California San Diego	[name]	120
	[name], MPH	
University of Pittsburgh	[name], MS	106
University of Pennsylvania	[name]	128
	[name], MPH	
John's Hopkins University	[name], MPH	159
University of Alabama	[name]	135
	[name]	
	[name] RN	

Name of Institution	Institution PI(s)	Number of women with	
		CF aged 18-45 years	
Harvard U/Boston	[name]	189	
Mount Sinai	[name]	51	

We anticipate that each site will be able to enroll 50% of eligible women ages 18-45 years into the study. We have chosen the lower age range because of estimated age of sexual debut among young women with CF is between ages 16-17 years (5) and it is expected that some women aged 18 will have started using contraception. We have chosen the upper age range of 45 years because of the lower life expectancy of women with CF compared to the general population and inherent bias that adults with CF who live past the currently life expectancy are most likely healthier than younger adults with CF (10).

Table 3: Age distribution goals for study enrollment

Age Distribution of Women with CF		
Age Range (years)	Approximate number of subjects planned	
18-35	383	
36-45	192	

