7.2. Eligibility Criteria

The study population will be women with CF who have used any form of contraception for protection against pregnancy or for treatment of dysmenorrhea, pelvic pain, abnormally heavy or prolonged menstrual bleeding, excessive uterine bleeding, endometriosis, acne, or amenorrhea.

Table 4: Full study inclusion and exclusion criteria

Inclusion Criteria
Females ages ≥ 18 and < 46 years at enrollment
Confirmed patients at one of the 10 participating CF centers (has been seen at least one time for a face-to-face
office visit at the CF center in the last 2 years)
CFFPR participant (noted as having a CFFPR ID number)
Has internet access
Has a functioning email addresses or may create a functioning email address at enrollment
Willing to consent to obtain request of their identified data from CFFPR
Willing to consent to their CF center to provide data related to contraceptive medication and DXA scan test results
as far back as 2013 in clinic EMR
Exclusion Criteria
Not in CFFPR
Non-functioning email address
History of organ transplant
Participant in pre-test phase of this study

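### The thromboembolism row of Table 5 adjusts for age only as above or below 35 and for BMI only as above or below 30, leaving avoidable age confounding in a safety comparison

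*Combined protocol and SAP*

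**What the plan says.** Section 9.3 makes Table 5 the adjustment set: "See Table 5 for confounders and covariates that we will use to adjust for the primary and secondary outcomes". In the venous/arterial thromboembolism row of Table 5 (section 7.5), the covariates are a BMI indicator at 30 or more followed by "Age > 35 years PMHx for thrombophilia Arterial/venous lines or ports Pmhx cancer Smoking". That row has no other age or BMI term, and no rationale appears beside the two cut-points.

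The coarsening is specific to this row. The pulmonary row lists uncategorised age, with the rationale "Lung function worsens as one ages", and uncategorised BMI. The bone row also lists both without a cut-point, and the liver row lists plain BMI. The Appendix requests date of birth and encounter-level BMI.

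Table 3 (section 7.1), under "Approximate number of subjects planned", gives 383 women aged 18-35 and 192 aged 36-45. Eligibility is "Females ages ≥ 18 and < 46 years at enrollment" (section 7.2). Outcome follow-up is earlier than enrollment. Section 9.3 gives the "start of the follow up period for outcome data (January 1, 2010", and section 5.0 takes the data "through the most recent data available from CFFPR (2018 or 2019". No section says at what date age is measured for adjustment.

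**The concern.** Thromboembolism is a secondary objective (section 4.2), and section 3.0 hypothesises harm from estrogen-containing oral methods. With age entered as a single indicator at 35, a 19-year-old and a 34-year-old are treated as having equal risk. If both method choice and clot risk vary with age between 18 and 35, that part of the confounding passes unadjusted into the comparison. The cohort is young, and younger still during the years in which outcomes are counted, so this is where most of the information lies. The exact values that would avoid the problem are already being requested.

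**Working it through.** **1. The plan's own figure.** 383 + 192 = 575, which agrees with the 575 in section 7.7. The share aged 18-35 at enrollment is 383/575 = 66.6%. The documents give no event count, age slope or age pattern of contraceptive use for thromboembolism, so everything on bias below rests on stated assumptions.

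**2. How many fall in the lower age class.** This depends on when age is measured.

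- *At enrollment:* 67%, from step 1.
- *On 1 January 2010:* section 7.0 gives "anticipated end date of pre-testing is July 2020", so enrollment starts about August 2020, some 10.6 years later. The oldest possible participant is then 46 - 10.6 = 35.4 years old on that date. Dating ages back from enrollment over about 15 months (section 7.1.1), only about 0.2% of women exceed 35.0 and none has reached 36. The covariate is almost constant.
- *Time-updated:* ages were simulated from Table 3 for 200,000 women, uniform within each band, dated back from enrollment in August 2020 to October 2021. Person-time was counted from age 18. For 2010-2018, 85% of person-time lies below age 36 and 81% at or below exactly 35.0. For 2010-2019 the shares are 83% and 79%.

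**3. How much age confounding remains.** Assume no true effect of hormonal use, odds of use proportional to exp(b × age), and clot rate proportional to exp(c × age). The crude rate ratio then differs from 1 only through age. The remaining fraction is

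f = ln(Mantel-Haenszel ratio stratified at the cut-point) / ln(crude ratio).

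Results for time-updated age, 2010-2018, with the upper class starting at 36:

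| b per year | c per year | Crude ratio | Adjusted ratio | f |
|---|---|---|---|---|
| -0.05 | 0.04 | 0.922 | 0.958 | 53% |
| -0.05 | 0.08 | 0.850 | 0.925 | 48% |
| -0.10 | 0.04 | 0.856 | 0.918 | 55% |
| -0.10 | 0.08 | 0.733 | 0.855 | 51% |
| +0.05 | 0.04 | 1.085 | 1.044 | 53% |

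For example, in the first row f = ln(0.958)/ln(0.922) = 0.043/0.081 = 0.53.

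Over both data end dates and both readings of the cut (36, or exactly 35.0), f runs from 38% to 55%, or about 40-55%. If age is taken at enrollment, f is about 26-31%. If it is taken on 1 January 2010, nearly all of the age confounding remains, because the indicator hardly varies.

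**4. Size on the ratio scale.** In the time-updated case with hormonal users younger, a true ratio of 1 appears as 0.96 down to 0.855, a shift of about 4-15%. With the sign of b reversed, the shift goes above 1 instead.

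**5. Limits of the calculation.** A pure step in risk at 35, flat on either side, would leave f = 0. Counting person-time from age 12 or 15 rather than 18 raises f to 46-64%.

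**The case against.** The strongest reply is that the bias is small beside the imprecision. The documents give no event count. Assuming 10 to 50 events split evenly between two groups, the 95% confidence factor is exp(1.96 × √(4/E)): 3.45 for E = 10 and 1.74 for E = 50. A 4-15% shift is well inside that. This stands, and it limits the importance of the point. It does not favour the cut-point, because continuous age uses the same number of parameters.

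It can also be said that no regression model is named for thromboembolism. Section 9.3 promises incidence rates, relative risks and confidence intervals, and section 6.0 says that the analysis plan is still being refined. That is true, but Table 5 is still declared to be the adjustment set, and this is the stage at which to change it.

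Four stronger readings are tempting, and the documents do not support them.

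- A reader might take 80-85% and about one half as facts about this study. They hold only for time-updated age, adult person-time and a log-linear effect.
- A reader might infer that the bias hides harm. That requires hormonal users to be younger, and no document gives their ages by method.
- A reader might infer that the BMI cut-point separates few women. No BMI distribution is given, and the plan's interest in low BMI belongs to the nutritional question, not to clot risk.
- A reader might assume that time-updated age, and BMI before method start, come free. Table 10 asks whether a clot ever occurred and does not clearly list its date. Registry data start in 2010 while exposure goes back to 2008, and non-users have no method start.

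**Conclusion.** The point holds for age, conditionally. The thromboembolism row uses a coarser age term than the other rows that list age, gives no reason, and leaves the date of age measurement open. Under a graded age effect, every reading examined leaves material confounding: about 26-31% (enrollment age), about 40-55% (time-updated) or nearly all (1 January 2010). The absolute shift in the time-updated case is modest, about 4-15% under the assumed slopes, and its direction is unknown. Only a pure step in risk at 35 would make the indicator sufficient, and nothing in the documents argues for one. For BMI the inconsistency between rows is real, but its effect cannot be quantified. This is an avoidable weakness in a secondary safety analysis and does not by itself invalidate the comparison.

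**What to change.** In the thromboembolism row of Table 5, replace the age indicator with continuous age at a stated reference date, and name that date. Use time-updated age only if the survey collects the date of the clot. Keep the cut-point at 35 for descriptive tables.

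This costs a wording change. It uses one parameter for one parameter and data already requested, and it removes the residual entirely if the age effect is log-linear and age is measured consistently. With a fixed reference date, attained age differs from the covariate by the same elapsed time for all women on a given calendar date, so the age gradient is still captured apart from calendar trends in method use.

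As a secondary change, list BMI as continuous, as in the other rows, using the first registry value in follow-up. That value does not depend on a method start, so it can also be defined for non-users and for methods begun before 2010. A linear BMI term imposes a shape of its own, so the reason for the chosen form should be stated in the row.
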